#### 10.2.1 Definitions

#### 10.2.1.1 iRECIST Definition

Responses assigned using iRECIST have a prefix of "i", which indicates immune response assigned using iRECIST. For example, "immune" complete response (iCR) or partial response (iPR), and unconfirmed progressive disease (iUPD) or confirmed progressive disease (iCPD) to differentiate them from responses assigned using RECIST 1.1. Similar nomenclature is used for stable disease (iSD). New lesions are assessed and sub-categorized into those that qualify as target lesions (new lesion, target) or non-target lesions (new lesion, non-target).

#### **10.2.1.2** Evaluation for Objective Response

Patients who exhibit objective disease progression prior to the end of cycle 1 will be considered evaluable for response. For all other patients, only those patients who have measurable disease present at baseline, have received at least one cycle of therapy, and have had their disease re-evaluated will be considered evaluable for response, whether it be unequivocal or iUPD, but not iCPD (before iCR, iPR or iSD). Patients who have lesions present at baseline that are evaluable, but do not meet the definitions of measurable disease, have received at least one cycle of therapy, and have had their disease re-evaluated will be considered evaluable for non-target disease. The response assessment is based on the presence, absence, or progression of the lesions (unequivocal or iUPD, but not iCPD, before iCR, iPR or iSD).

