#### 11. STATISTICAL CONSIDERATIONS

This is a pilot study for which the initial aim was to accrue 20 paediatric patients with bMMRD tumours. Following amendment, the study inclusion criteria will be expanded to include those with hypermutant tumours (as determined by estimation of TMB by targeted gene sequencing), as well as those with CMMRD, including bMMRD tumours, and consequently the total enrollment will be increased to 50 patients.

The primary objective is to determine the ORR as well as to estimate the efficacy of nivolumab in patients with hypermutant tumours. The study is predicated on the hypothesis that patients with hypermutated tumours will derive greater benefit from nivolumab than those without; however, the relevant threshold of TMB is not yet established. Consequently, in this pilot study, patients will be recruited into two cohorts depending on TMB. This will provide the opportunity to treat patients with a relatively low TMB ( $\geq$ 5 to <10/Mb, estimated ~15% of tumors) to assess for responses to nivolumab, while a separate cohort for patients with TMB ( $\geq$ 10/Mb, estimated ~5% of tumors) will ensure that overall study enrollment is not dominated by patients with lower TMB.

A Simon two-stage design will be used within each cohort.

For cohort A (TMB ( $\geq$ 5 to <10/Mb), the null hypothesis that the true response rate is only 10% will be tested against a one-sided alternative. In the first stage, 10 patients will be accrued. If there are 1 or fewer responses in these 10 patients, the cohort will be closed. Otherwise, 10 additional patients will be accrued for a total of 20. The null hypothesis will be rejected if 5 or more responses are observed in 20 patients. This design yields a type I error rate of 0.05 and power of 85% when the true response rate is 35%. Accrual to this cohort will stop if evidence accumulates that the efficacy is lower than the specified acceptable levels. If five or more ( $\geq$ 5) patients experience objective responses (CR+PR), then we will conclude that Nivolumab is sufficiently active in patients with TMB  $\geq$ 5 to <10/Mb to warrant recommendation for continued investigation.

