For Cohort B (TMB  $\geq$ 10/Mb), in the first stage, 10 patients will be accrued. If there are 1 or fewer responses in these 10 patients, the cohort will be closed. Otherwise, 20 additional patients will be accrued for a total of 30. The null hypothesis will be rejected if 6 or more responses are observed in 30 patients. This design yields a type I error rate of 0.05 and power of 80% when the true response rate is 30%. Accrual to this cohort will stop if evidence accumulates that the efficacy is lower than the specified acceptable levels. If six or more ( $\geq$ 6) patients experience objective

responses (CR+PR), then we will conclude that Nivolumab is sufficiently active in patients with  $TMB \ge 10/Mb$  to warrant recommendation for continued investigation.

Patients already recruited to study at the time of amendment will be retrospectively allocated to the appropriate cohort based on TMB. It is anticipated that most of these patients with CMMRD will have TMB ≥10/Mb and will therefore fall into cohort B. Any patients with CMMRD for whom TMB is not available will be analyzed separately in Cohort C.

In order to make decisions about further exploring the use of nivolumab in this patient population, a likelihood Bayesian analysis will also be used to provide estimates of likely effect sizes based on results from this pilot study. Posterior probability distributions for response rate will be plotted, using non-informative priors.

For example, in Cohort A, a response in 5 of 20 patients (estimate response rate 0.25), indicates a probability that the true RR is >0.2 of 0.77; while there is only a 0.01 probability that the true RR is <0.1. Similarly, for Cohort B, a response in 6 of 30 patients (estimated RR 0.2), indicates a probability that the true RR is >0.2 of 0.57; while there is a 0.03 probability that the true RR is <0.1.

Patients who are evaluable for objective response are those who meet the definition as per *Section 10.2.1.2*.

All enrolled patients who received at least one dose of any study drug will be evaluable for safety. A safety evaluation will be performed by the Safety Committee after Patient 1 Cycle 1, Patient 4 Cycle 1, Patient 7 Cycle 1, and Patient 10 Cycle 1. Enrollment will be held after each time point until a safety evaluation of adverse events and serious adverse events confirms it is safe to resume enrollment.

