# 13. PROCEDURES FOR DISCONTINUATION OF A PATIENT FROM INVESTIGATIONAL PRODUCT

## 13.1 Procedures for Withdrawal from Study

Patient / Legally Acceptable Representative (LAR; such as a parent or guardian, as applicable) are at any time free to withdraw from study (study medication and assessments), without prejudice to further treatment (withdrawal of consent). Such patients and/or their legal guardians will always be asked about the reason(s) and the presence of any adverse events. If possible, they will be seen and assessed by an investigator. Adverse events will be followed up.

Withdrawn patients who meet the criteria to be evaluable for objective response or non-target response as per *Section 10.2.1.2* will not be replaced. Patients who withdraw from the study prior to meeting the criteria to be evaluable in *Section 10.2.1.2* will be replaced on study.

If a patient does not return for a scheduled visit, every effort should be made to contact the patient and/or their legal guardians. In any circumstance, every effort should be made to document patient outcome and reason for withdrawal, if possible. The investigator should request the patient return for a final visit, if applicable and follow-up with the patient regarding any unresolved adverse events.

If the patient and/or their legal guardians withdraw from the trial and also withdraw consent for disclosure of future information, no further evaluations should be performed, and no additional data should be collected. The Study Chair or Co-Chair may retain and continue to use any data collected before such withdrawal of consent.

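### Section 10.2.1.2 words response evaluability so that some confirmed progressors (iCPD) literally fall outside the ORR denominator; the clause looks like a misplaced response-sequencing rule and should be moved

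*Protocol*

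**What the plan says.** Section 10.2.1.2 of the protocol defines who is evaluable for objective response in three steps.

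- Patients with objective progression before cycle 1 ends are evaluable, without condition.
- All others need measurable disease at baseline, at least one cycle of treatment and a re-evaluation. Those patients "will be considered evaluable for response, whether it be unequivocal or iUPD, but not iCPD (before iCR, iPR or iSD".
- Patients with only non-measurable disease are evaluable for non-target disease on similar terms. A separate sentence then bases their response assessment on presence, absence or "progression of the lesions (unequivocal or iUPD, but not iCPD, before iCR, iPR or iSD".

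Two other places depend on this definition. Section 11 states: "Patients who are evaluable for objective response are those who meet the definition as per" Section 10.2.1.2. Section 13.1 provides for replacement: "Patients who withdraw from the study prior to meeting the criteria to be evaluable in" that section are replaced, while withdrawn patients who have met the criteria are not.

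The decision rules in Section 11 are simple counts. For Cohort A, "the null hypothesis that the true response rate is only 10% will be tested against a one-sided alternative"; at stage 1, "If there are 1 or fewer responses in these 10 patients, the cohort will be closed"; and at the end, "The null hypothesis will be rejected if 5 or more responses are observed in 20 patients". Cohort B has the same stage 1 rule and rejects at 6 or more responses in 30.

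**The concern.** In the sentence on measurable disease, the grammatical subject is the patient and the predicate is being evaluable. As written, the clause therefore decides who is counted, not what response is assigned, and it does so by result. A patient whose first scan shows unconfirmed progression (iUPD), and whose next scan confirms it (iCPD), has had a treatment failure. Under the literal text that patient is not evaluable for response unless the first sentence of the section applies.

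If those patients leave the denominator because they failed, the ORR, which is the primary objective, is estimated too high. If their places are then refilled, the 1/10, 5/20 and 6/30 rules are applied to an enriched set, and 10% is no longer the response rate being tested.

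The protocol also disagrees with itself. Table 7 in Section 10.7.1 gives the sequence iUPD then iCPD a best response of PD, which is a classified failure. In an open-label single-arm study, the choice between these two treatments of the same patient should not be left open until results are known.

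**Working it through.** **1. What the words mean elsewhere.**

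| Place | Use of the iUPD/iCPD wording |
|---|---|
| 10.2.3, target lesions | iCR, iPR or iSD may be assigned after iUPD provided iCPD was not confirmed |
| 10.2.5, non-target assessment | iUPD, but not iCPD, may come before iCR |
| 10.2.7 | Earlier iUPD does not bar a later response or best overall response, unless the next assessment gives iCPD |
| Table 7 | iUPD then iCPD has best response PD |
| 10.2.1.2, non-target sentence | Attached to how response is assessed |
| 10.2.1.2, measurable-disease sentence | Attached to who is evaluable |

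Only the last row turns the ordering rule into a rule about membership of the analysis set.

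**2. Who is exposed.** Footnote 12 of the Section 8.2 calendar puts the first disease evaluation at the end of cycle 1, with a window of −7 days, and then every two months. Progression found on an early in-window scan can fall under the first sentence of 10.2.1.2, so that patient is evaluable. A patient with stable disease or better on the first scan has iSD before any iCPD and is also evaluable. The exposed group is therefore iRECIST-assessed patients whose first-scan iUPD is not treated as early progression and is then confirmed with no iSD, iPR or iCR in between. The text does not say whether a scan done exactly at the end of cycle 1 counts as early. iCPD is not a category in the CNS, AML, ALL or lymphoma criteria.

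**3. The plan's own figures.** Inputs from Section 11: n1 = 10, stop at 1 or fewer; Cohort A rejects at 5 or more of 20, Cohort B at 6 or more of 30. Section 11 states no null rate for B, so 10% is assumed. With rejection count r:

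P(reject) = Σ over x ≥ 2 of P(X1 = x) × P(X2 ≥ r − x), where X1 ~ Bin(10, p) and X2 ~ Bin(10, p) for A or Bin(20, p) for B.

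Cohort A at p = 0.10:

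- x = 2: 0.1937 × 0.0702 = 0.0136
- x = 3: 0.0574 × 0.2639 = 0.0151
- x = 4: 0.0112 × 0.6513 = 0.0073
- x ≥ 5: 0.0016
- Total: 0.0376

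The same formula gives 0.0525 for B at 0.10. Power is 84.3% for A at 35% (stated 85%) and 81.5% for B at 30% (stated 80%). The stated designs are reproduced closely enough.

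**4. Exclusion without refilling.** The rules count responses, and dropping non-responders adds none, so Type I error does not rise. Only the estimate moves:

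- Cohort A, four dropped: 5/20 = 25% becomes 5/16 = 31%.
- Cohort B, six dropped: 6/30 = 20% becomes 6/24 = 25%.

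**5. Exclusion with refilling.** Let f be the share of a cohort excluded, all of them non-responders. The response rate among counted patients is 0.10/(1 − f). The documents do not give f, so a range is shown.

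| f (assumed) | 0.10/(1 − f) | Type I error, A | Type I error, B |
|---|---|---|---|
| 0 | 0.100 | 0.038 | 0.053 |
| 5% | 0.105 | 0.046 | 0.064 |
| 10% | 0.111 | 0.055 | 0.079 |
| 20% | 0.125 | 0.084 | 0.121 |
| 30% | 0.143 | 0.130 | 0.187 |
| 50% | 0.200 | 0.334 | 0.452 |

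For a whole cohort, f is the iRECIST-assessed share times the exposed share within it. If half the cohort were assessed by iRECIST and 20% of those were exposed (both illustrative), f = 0.50 × 0.20 = 10%.

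**The case against.** The best defence is that the clause was never meant as a denominator rule. Sections 10.2.3, 10.2.5 and 10.2.7 use the same idea for sequencing, and so does the non-target sentence of 10.2.1.2 itself. Table 7 classes these patients as PD. Sections 10.4.3 and 10.5 say that each patient gets a best response for the analysis of treatment effect. No passage says outright that confirmed progressors are removed from the ORR. This stands as evidence of intent, and it is why the clause is best seen as misplaced. It does not change what the evaluability sentence says, or that Section 11 points to that sentence.

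A second defence is that iCPD requires an earlier iUPD. At the first re-evaluation the patient has iUPD, which the clause accepts, and nothing says evaluability is later withdrawn. That reading is reasonable, but the exception for iCPD then has no effect on membership at all, which again shows it is in the wrong place.

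A third defence concerns size, and it stands. A reader might infer that confirmed progressors as a class leave the denominator and that Type I error is therefore inflated. The documents do not support that. The first sentence of 10.2.1.2 keeps early progressors, prior iSD keeps others, and several tumour types are not assessed by iRECIST. Section 13.1 replaces only patients who withdraw before becoming evaluable. Section 11 speaks of patients accrued, and Section 3.1.1 caps the cohorts at 20 and 30. Refilling is possible, since Section 13.2 lists progression beyond 12 weeks among its withdrawal and discontinuation criteria, but no text requires it for these patients.

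**Conclusion.** The evaluability sentence is wrong as written and conflicts with Table 7. Applied literally, it biases the primary ORR upward. At the Cohort A threshold the shift is about 6 percentage points if four patients are dropped (25% to 31%).

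Inflated Type I error is a conditional consequence, not an established one. It needs the excluded patients to be refilled, a value of f that the documents do not supply, and, for Cohort B, an assumed null of 10%. Because the clause touches only part of the iRECIST-assessed patients, a whole-cohort f towards the lower end of the range is more plausible. At f between 5% and 10% the error would be 0.046 to 0.055 in A and 0.064 to 0.079 in B. The values at 30% and 50% show direction and should not be taken as expected.

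The point is a wording correction to the definition behind the primary endpoint, best made before the stage 1 and final rules are applied. It does not show that the two-stage design is unsound.

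**What to change.** In Section 10.2.1.2, delete the iUPD/iCPD clause from the measurable-disease sentence and add:

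*Every patient who progresses early or whose disease is re-evaluated is evaluable for response, whatever the result. iCPD without a prior qualifying iCR or iPR is a non-response and stays in the denominator.*

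Move the ordering rule, including the similar words in the non-target sentence, to the best overall response text (Section 10.4.1) as a response-assignment rule only: a response may follow iUPD but not iCPD. Sections 11 and 13.1 can keep their cross-references, which will then point to a definition that does not depend on outcome and agrees with Table 7.

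The cost is a short amendment to the wording. No assessment, sample size or decision threshold changes. The reported ORR may be slightly less favourable than under the literal text.

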#### **10.2.2** Disease Parameters

#### 10.2.2.1 Measurable Disease

Measurable lesions are defined as those that can be accurately measured in at least one dimension (longest diameter to be recorded) as  $\geq 20$  mm by chest x-ray, as  $\geq 10$  mm with CT scan or  $\geq 10$  mm with calipers by clinical exam for a maximum of five lesions (two per organ). All other disease is considered non-target (must be  $\geq 10$  mm in short axis for nodal disease). All tumour measurements must be recorded in millimeters (or decimal fractions of centimeters). New lesions (as per iRECIST) are assessed as per RECIST 1.1 criteria, but are recorded separately on the case report form (and not included in the sum of lesions for target lesions identified at baseline).

## 10.2.2.2 Malignant Lymph Nodes

To be considered pathologically enlarged and measurable, a lymph node must be  $\geq 15$  mm in short axis when assessed by CT scan (CT scan slice thickness no greater than 5 mm). At baseline and in follow-up, only the short axis will be measured and followed.

#### 10.2.2.3 Non-measurable Disease

All other lesions (or sites of disease), including small lesions (longest diameter <10 mm or pathological lymph nodes with  $\geq$  10 to <15 mm short axis), are considered non-measurable disease. Bone lesions, leptomeningeal disease, ascites, pleural/pericardial effusions, lymphangitis cutis/pulmonitis, inflammatory breast disease, and abdominal masses (not followed by CT or MRI), are considered as non-measurable.

Note: Cystic lesions that meet the criteria for radiographically defined simple cysts should not be considered as malignant lesions (neither measurable nor non-measurable) since they are, by definition, simple cysts. 'Cystic lesions' thought to represent cystic metastases can be considered as measurable lesions, if they meet the definition of measurability described above. However, if non-cystic lesions are present in the same patient, these are preferred for selection as target lesions.

## 10.2.3 Assessment of Target Lesions

All measurable lesions up to a maximum of two (2) lesions per organ and five (5) lesions in total, representative of all involved organs, should be identified as target lesions and recorded and measured at baseline. Target lesions should be selected on the basis of their size (lesions with the longest diameter), be representative of all involved organs, but in addition should be those that lend themselves to reproducible repeated measurements. It may be the case that, on occasion, the largest lesion does not lend itself to reproducible measurement in which case the next largest lesion that can be measured reproducibly should be selected. A sum of the diameters (longest for non-nodal lesions, short axis for nodal lesions) for all target lesions will be calculated and reported as the baseline sum of diameters (iSOD). If lymph nodes are to be included in the sum, then only the short axis is added into the sum. The baseline sum diameters will be used as reference to further characterize any objective tumour regression in the measurable dimension of the disease.

If iUPD criteria were met on the basis of progression in the target or non-target disease, or the appearance of new lesions, then RECIST 1.1-assigned progression in another lesion category in the confirmatory scan also confirms iCPD. Each time point response is based on the assessment of target lesions, non-target lesions, and new lesions. For time point response (as per iRECIST criteria), the management of lymph nodes, lesions that become too small to measure, lesions that split or coalesce, and the definition of complete response, partial response, stable disease, and progressive disease are clearly outlined throughout *Section 10.2* (Seymour, 2017).

For target lesions, iCR, iPR, and iSD can all be assigned after iUPD has been documented, as long as iCPD was not confirmed. iUPD is defined by RECIST 1.1 criteria for progressive disease and can be assigned multiple times as long as iCPD is not confirmed at the next assessment. Progression is confirmed in the target lesion category if the next imaging assessment after iUPD (4–8 weeks later) confirms a further increase in sum of measures of target disease from iUPD, with an increase of at least 5 mm. However, the criteria for iCPD (after iUPD) are not considered to have been met if CR, PR or SD criteria (compared with baseline and as defined by RECIST 1.1) are met at the next assessment after iUPD (Seymour, 2017). The status is reset (unlike RECIST 1.1, in which any progression precludes later complete response, partial response, or stable disease). iCR, iPR, or iSD should then be assigned; and if no change is detected, then the time point response is iUPD (Seymour, 2017).

## 10.2.4 Assessment of Non-Target Lesions

All other lesions (or sites of disease) including any measurable lesions over and above the five (5) target lesions should be identified as non-target lesions and should also be recorded at baseline. Measurements of these lesions are not required, but the presence, absence, or in rare cases unequivocal progression of each should be noted throughout follow-up.

## 10.2.5 Assessment of New Malignant Lesions

The assessment of non-target lesions at each time point follows similar principles. iUPD (but not iCPD) can have been documented before iCR or when the criteria for neither CR nor PD have been met (referred to as non-iCPD/non-iUPD) and can be assigned several times, as long as iCPD was not confirmed. iUPD is defined by RECIST 1.1 criteria; however, iUPD can be assigned

multiple times as long as iCPD is not confirmed at the next assessment. PD in the non-target lesion category is confirmed if subsequent imaging, done four to eight weeks after iUPD, shows a further increase from iUPD.

The criteria for iCPD are not judged to have been met if RECIST 1.1 criteria for complete response or non-iCR/non-iUPD are met after a previous iUPD. The status is reset (unlike RECIST 1.1) and iCR, or non-iCR/non-iUPD is assigned; if no change is detected, the time point response is iUPD (Seymour, 2017). Changes in the largest diameter (unidimensional measurement) of the tumour lesions, but the shortest diameter of malignant lymph nodes are used in the RECIST v.1.1 criteria. In view of the potential for patients treated with immunotherapies to show early signs of disease progression, but ultimately to benefit from treatment, patients with evidence of progressive disease will also be evaluated using iRECIST criteria and may continue on study provided criteria outlined below are met.

RECIST 1.1 defines the appearance of new malignant lesions as denoting true disease progression, providing that other lesions (artefacts or benign intercurrent disease) are appropriately assessed and discounted if not malignant. If a new lesion is equivocal, for example because of its small size, continued therapy and follow-up assessment will clarify whether it represents truly new disease. If repeat scans confirm there is definitely a new lesion, then progression should be declared using the date of the initial scan (Eisenhaur, 2009).

Aspects of new lesion assessment unique to iRECIST, include if a new lesion is identified (thus meeting the criteria for iUPD) and the patient is clinically stable, treatment should be continued. New lesions should be assessed and categorised as measurable or non-measurable using the RECIST 1.1 principles. a maximum of five lesions, no more than two per site, at least 10 mm in long axis (or 15 mm in short axis for nodal lesions), and recorded as New Lesions-Target (NLT) and New Lesion-Non-Target (NLNT) to allow clear differentiation from baseline target and non-target lesions. New lesions may either meet the criteria of NLT or NLNT to drive iUPD (or iCPD). However, the measurements of target lesions should not be included in the sum of measures of original target lesions identified at baseline. Rather, these measurements will be collected on a separate table in the case record form.

Results in UPD but iCPD is only assigned on the basis of this category if at next assessment additional new lesions appear or an increase in size of new lesions is seen ( $\geq 5$  mm for sum of new

lesion target or any increase in new lesion non-target). The appearance of new lesions when none have previously been recorded, can also confirm iCPD.

Other measurable and non-measurable lesions are recorded as new lesion non-target. New lesions do not need to meet the criteria for new lesion target to result in iUPD (or iCPD); new lesion non-target can also drive iUPD or iCPD. PD is confirmed (iCPD) in the new lesion category if the next imaging assessment, done at four to eight weeks after iUPD, confirms additional new lesions or a further increase in new lesion size from iUPD (sum of measures increase in new lesion target ≥5 mm, any increase for new lesion non-target in the absolute value of the sum of NLT or an increase (but not necessarily unequivocal increase) in the size of NLNT lesions or the appearance of additional new lesions.

